Current evidence-based nutritional guidelines for CD, arise mainly from epidemiological data and generally suggest a "healthy diet", characterized by an increased consumption of nutrient-dense foods along with a restricted intake of saturated and trans-fats, emulsifiers, thickeners, processed foods, unpasteurized dairy. According to the Dietary Guidance from the International Organization for the Study of Inflammatory Bowel Diseases (IOIBD), consensus was not reached for pasteurized dairy consumption among patients with CD. Based to evidence from epidemiology and animal models, the authors clarify that it is prudent for Crohn's disease patients to avoid lactose, given that lactase deficiency and lactose intolerance is common among patients with IBD. It was also noted that it could be prudent to reduce dairy fat and processed dairy rich in maltodextrins and emulsifiers (7). To date, no clear and strong recommendation can be given to follow a specific diet for inducing remission in patients with active CD, whereas the importance of a personalized nutritional approach is highlighted (8). Exclusive Enteral Nutrition (EEN) is the only well-established dietary therapy in CD and is commonly used for the induction of remission in mild to moderate pediatric CD (8-9, 12-13). Evidence according to EEN efficacy in adults is not consistent, which could more likely be explained by the compliance difficulty rather that by mechanistic differences (10-12). It is of interest, that fecal inflammation increases rapidly after food re-introduction following EEN in children (14). In this context, partial enteral nutrition (PEN) has sparked scientific interest as a possible maintenance dietary strategy. PEN has been shown to be beneficial in maintaining remission, but poor compliance due to low formula palatability and patients' fatigue remains an important barrier in the clinical practice. Moreover, PEN is inferior to EEN in inducing remission (13,15). Sigall Boneh and her colleagues evaluated a novel dietary intervention that combined PEN with an elimination diet (19). The Crohn's disease exclusion diet (CDED) is a whole-food, high protein, low saturated fat, low taurine, low heme, low food additives diet with exposure to fiber mainly from fruits, vegetables and complex carbohydrates. More specifically, CDED eliminates specific dietary components hypothesized to induce dysbiosis and appears to be effective in inducing and maintaining remission both in pediatric and adult population (16-19).

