Patients will be randomly assigned 1:1 to either CDED plus PEN plus dairy products or PEN plus usual nutritional care. In detail, half of the patients in remission will follow the first stage diet (CDED+PEN) for 4 weeks and will continue with CDED + PEN + dairy products for another 4 weeks. The other half will be given PEN plus the usual advice for a healthy dietary pattern. PEN will cover the 50% of total energy requirements for the first 4 weeks and the 25% during the second 4 weeks. Half of the patients with active disease will follow the first stage diet (CDED + PEN 50%) for 6 weeks and then, the responders will continue with adding the dairy product while PEN will cover 25% of the total energy requirements, for 4 more weeks. The other half will be given PEN plus the usual advice for a low residue diet. Low lactose, low fat and low additive dairy foods will be given, namely Greek yogurt 2% fat and light yellow cheese with 10-12% fat, in calculated portions to meet tailored energy, protein and calcium requirements. After the end of the intervention period, patients will be advised to reintroduce foods that were eliminated and to follow a maintenance diet. All participants will attend study visits at the beginning, in the middle (week 8 or week 10, for patients entering the study in remission or with active symptoms, respectively) and at the end of the study, at which points questionnaires will be completed, anthropometric measurements will be conducted and biological samples will be collected. The last follow-up will take place in week 24. In the meanwhile, phone calls by a researcher dietitian will be held to assess adherence and support the patients.24-hour diet recallsand the modified Medication Adherence Report Scale (MARS) questionnaire (16) will be used to address compliance along with the physician's assessment.

At length, our methodological approach includes:

i) Anthropometry

- (1) Weight (kg) measurement, [Time Frame: Baseline, week 4, week 8 (Baseline, week 6, week 10 for patients entering the study with active disease), week 24]
- (2) Height (m) measurement, [Time Frame: Baseline],
- (3) Body mass index (BMI) (kg/m²) calculation
- (4) Waist, neck and midarm circumferences (cm), triceps skinfold (mm) measurement [Time Frame: Baseline, week 8/w10]
- (5) Body composition analysis (Fat mass, fat %, fat free mass, phase angle)
 by Bioelectrical Impedance Analysis (BIA) [Time Frame: Baseline, week
 8/10]

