- (6) Handgrip strength (kg) assessment by dynamometer [Time Frame: Baseline, week 8/w10]
- Dietary habits assessment, using a semi-quantitative food frequency questionnaire (FFQ), to assess dietary habits and adherence to the Mediterranean diet (MD-score) [Time Frame: Baseline, week 24] and 24-

recalls [Time Frame: Baseline, week 2/w3, week 4/w6, week 6/w8, week 8/w10]

- iii) Physical activity assessment, using HPAQ questionnaire [Time Frame: Baseline, week 8/w10]
- iv) Health-related quality of lifeassessment, defined by the selfadministered 32-item Inflammatory Bowel Disease questionnaire (IBDQ) score. Higher IBDQ scores indicate better outcomes. Clinical response defined as increase ≥16 points [Time Frame: Baseline, week 8/w10]
- v) Medical history (e.g.,prior GI surgery, comorbidities) data collection and disease activity assessment by the HBI. Clinical response is defined as baseline HBI score decrease of ≥ 3[Time Frame: Baseline, week 4/w6, week 8/w10]
- vi) **Blood and Feacal samples collection** by specializes staff [Time Frame: Baseline, week 4/w6, week 8/w10]
 - (1) **Blood samples analysis** by the hospital's lab to estimate serum **CRP** and **albumin**
 - (2) Feacal samples analysis by certified labs to estimate Feacal calprotectin concentration (μ g/g)
- vii) Nutrition education according to the intervention principals and prescription of nutritional supplements (liquid formulas-PEN) [Time Frame: Baseline]. Support line for patients' support will be available.
- viii)**Handle-analysis** of the questionnaires and **data entry** in electronic databases [Microsoft® Excel, IBM SPSS Statistics®, Nutritionist Pro®]
- ix) Statistical analysis/interpretation of results.

Eligibility Criteria:

Inclusion Criteria:

- Participants must have an established diagnosis of CD
- Individuals able to give informed consent and willingness to participate Exclusion Criteria:
 - Age < 18 years old
 - Previous extensive bowel resection
 - Reported pregnancy or lactation
 - Current stoma or abscess
 - Clinically significant stricture
 - Introduction of or change in dose of drug therapy within the past 8 weeks

- Comorbidities including diabetes or coeliac disease, or other concomitant serious comorbidity e.g. significant psychiatric, hepatic, renal, endocrine, respiratory, neurological, cardiovascular, neoplastic or other autoimmune disease
- Food allergies or intolerances, which do not permit participation in the study

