- Any proven current infection such as positive stool cultures or positive tests for parasites or C. difficile.

The proposed project has a duration of thirty-six (36) months. The 1st phase that has already been completed included preparation and printing of questionnaires, creation of recipes based on the principles of the dietary intervention. The recruitment process is anticipated to start in September 2022 and to be completed by March 2024.

Statistical Analysis Plan (SAP)

Based on pilot data (18) we performed a sample size calculation using the GPower 3.0.10 software (http://www.softpedia.com/get/Science-CAD/G-Power.shtml). A sample of 140 individuals is sufficient to achieve statistical power > 80 %, at a significance level of a = 0,05 for two-sided statistical tests. All continuous variables will be assessed for normality with the Kolmogorov–Smirnov test (cutoff p < 0.01), to use parametric or non-parametric tests, as appropriate. Chi-squared or Fischer's test will be used to analyze categorical variables. Continuous variables will be analyzed by using Mann Whitney U test and t-test for paired-samples or the Wilcoxon signed rank). For paired measures (e.g. FC concentration) before and after the intervention, we will calculate the percentage change for each patient relative to baseline. Logistic regression models will be used to explore how age, sex, phenotypic factors (disease location and activity), MD-scoreat baseline, adherence and intervention grouping would contribute to significant HBI or FC concentration drop.

Bibliography:

3;396(10256):e56]. *Lancet*. 2017;390(10114):2769-2778. doi:10.1016/S0140-6736(17)32448-0

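### The SAP tests FC and HBI on a single follow-up value with no missing-data rule, and no listed method lets the scheduled week 4/6 reading inform a missing week 8/10 value

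*Combined protocol and SAP*

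**What the plan says.** The Statistical Analysis Plan is one paragraph.

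- **Continuous outcomes.** "Continuous variables will be analyzed by using Mann Whitney U test and t-test for paired-samples or the Wilcoxon signed rank". For paired measures such as FC, it adds each patient's percentage change from baseline.
- **Binary outcomes.** Chi-squared or Fisher's exact test, and logistic regression for a significant HBI or FC drop.
- **Not stated.** It gives no rule for missing values, no analysis population, no dropout allowance, no model that takes several visits together, and no visit for the value after the intervention.

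Design and Methods, item vi, schedules blood and faecal samples "by specializes staff [Time Frame: Baseline, week 4/w6, week 8/w10"; item v gives the same three times for HBI. The visit paragraph has all participants attend at the start, at week 8 or 10 and at the end, with biological samples collected. It does not name week 4/6. Among diet-arm patients with active disease, it has only the responders continue into the dairy stage after week 6.

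The Background names "poor compliance due to low formula palatability", together with fatigue, as a barrier to PEN in practice.

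**The concern.** A percentage change, a paired test or an observed drop cannot be computed without the follow-up value. Where the plan gives no rule, standard software omits the patient, and the analysis becomes a comparison of patients with complete data. That comparison is protected by randomisation only if loss is unrelated to outcome or acts alike in both arms.

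Both arms receive PEN, and one adds an exclusion diet, so unequal loss is possible. If patients who respond poorly are lost more often from one arm, that arm looks better than it is. The trial plans a reading that could reduce this error, because week 4/6 FC should predict week 8/10 FC, but a test on one follow-up value ignores it for any patient whose later value is missing. With no rule written down, the handling may also be chosen after the data have been seen.

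**Working it through.** **1. The plan's own figure.** The SAP states: "A sample of 140 individuals is sufficient to achieve statistical power > 80" percent, two-sided alpha 0.05. It gives no effect size, SD, rates, endpoint or test, so 140 cannot be reproduced. Solving backwards with 70 per arm (1:1 allocation):

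- d = (1.960 + 0.842) × √(2/70) = 0.474 for 80% power.
- If 140 was sized at this d and 20% of values are missing (assumed), 56 per arm remain, and power = Φ(0.474 × √(56/2) − 1.960) = Φ(0.55), about 71%.

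**2. Which methods need which values.**

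| Method in the SAP | Needs | Patient with no week 8/10 value, if that visit is analysed |
|---|---|---|
| Paired t, Wilcoxon signed rank, percentage change | baseline and one follow-up | omitted |
| Mann-Whitney U | one value per patient (end value or change) | omitted |
| Chi-squared, Fisher, logistic on a drop | a response status | omitted unless a rule assigns a status; none is stated |

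No row uses week 4/6 to inform a missing week 8/10 value.

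**3. Binary illustration.** Assume 40% true response in both arms, every lost patient a non-responder, and loss of 25% on diet and 10% in control.

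- Patients with data: 0.40/0.75 = 53.3% against 0.40/0.90 = 44.4%, a false difference of 8.9 points.
- Missing counted as non-response: 40% against 40%.

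**4. FC illustration.** Simulated log FC with no true effect and 70 per arm. Diet-arm loss is more likely when the week 4/6 change is poor; control loss is 10% at random. Rates, correlations (about 0.6 to 0.7) and dependence are assumptions. Two separate set-ups gave:

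| Diet-arm loss | False benefit in patients with data (SD) | Type I error |
|---|---|---|
| 20% | 0.08 to 0.10 | 8.2 to 8.7% |
| 30% | 0.14 to 0.19 | 12.5 to 18.2% |

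The lower figure in each row is in SDs of log FC at one visit, tested by Mann-Whitney. The upper is in SDs of change in log FC, tested by t-test. At 25% loss, runs gave 0.10 to 0.15 SD and about 10 to 13% error. A likelihood analysis using both follow-up visits brought the bias to about zero when all loss came after week 4/6. With the same response-linked mechanism and 20% loss in both arms, the comparison of patients with data showed no bias (error 4.5%).

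**5. When patients leave before week 4/6.** They have no mid-study value to use. At 25% against 10% loss:

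| Share of loss before week 4/6 | Remaining bias of the likelihood analysis (SD) |
|---|---|
| none | 0.00 |
| half | 0.04 to 0.05 |
| four-fifths | 0.07 to 0.08 |

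**6. Precision with equal, random loss.** Take 56 per arm, SD 1 at each visit, and baseline-to-end correlation r.

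- Unadjusted change: SE = √(4(1 − r)/56), which is 0.189 at r = 0.5 and 0.169 at r = 0.6.
- Baseline-adjusted: SE = √(2(1 − r²)/56), which is 0.164 and 0.151.

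A simulation that also used week 4/6 gave about 0.19 falling to 0.16, so most of this gain comes from baseline adjustment.

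**The case against.** Several points against the concern stand.

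- **Silence is not a rule to delete.** A reader might infer that every FC and HBI test requires a before-after pair. Mann-Whitney can be run on end values without a baseline, and the binary analyses could count missing patients as non-responders. The SAP neither says this nor excludes it.
- **Stopping the diet is not a missing sample.** A reader might infer that patients who quit the diet vanish from the result. The visit paragraph plans attendance and samples for all participants, so a patient who quits but attends still contributes. The least certain follow-up is that of diet-arm patients with active disease who do not respond by week 6.
- **Week 4/6 may be used for something.** No visit is attached to the value after the intervention. Week 4/6 ends the first diet stage, so it could be the endpoint for the primary goal, and it is the natural reference for the dairy aim. It would then be wrong to call the reading unused, and there would be no earlier follow-up value to borrow from.
- **The cited barrier is common to both arms.** Poor PEN compliance does not show that loss will be higher on the exclusion diet or tied to poor response there.
- **The correction is partly built into the illustration.** When loss depends on an observed week 4/6 value, a model using that value must do well. Step 5 shows how far this weakens when loss is early.

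These points limit the claim about direction and size. They leave in place the absence of any missing-value rule, and the fact that no listed method draws on week 4/6 when the later value is missing.

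**Conclusion.** The point holds in a limited form, as an improvement that should be made before analysis. By default the plan analyses only patients who have the chosen follow-up value, and it sets aside information it already intends to collect. Whether this biases the result depends on loss that the documents do not describe. Under assumed response-linked loss of 25% on diet against 10% in control, the false benefit is about 0.10 to 0.15 SD with 10 to 13% type I error. If the mechanism and rate are the same in both arms, it is nil.

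The documents do not support a statement that the trial will be biased toward the diet, or that using week 4/6 would remove most of any bias. The second depends on patients staying at least until that visit. The precision gain does not depend on unequal loss: at 20% random loss the standard error falls from about 0.19 to 0.16 SD under assumed correlations of 0.5 to 0.6.

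**What to change.** Amend the SAP as follows.

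1. Analyse log FC with a mixed model for repeated measures: arm, visit (week 4/6, week 8/10), arm by visit, baseline log FC and entry group (remission or active). Include every randomised patient with any post-baseline value. Name the visit at which the arms are compared. Use the same model for HBI on its own scale.
2. In the binary response outcomes, count a patient with no HBI or FC value at the analysed visit as a non-responder.
3. State that the visits and samples planned for all participants continue after a patient stops the diet, and that this includes week 4/6, which the visit paragraph omits.
4. Tabulate missing FC and HBI values by arm and visit.
5. Add one sensitivity analysis that includes patients with no post-baseline value, for example multiple imputation with missing values made worse by stated amounts.

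**Cost.** SAP wording and a standard model in SPSS, which the protocol already names. Item 3 should be settled early, because missed samples cannot be recovered. The model assumes data are missing at random and corrects only part of the bias from early loss, which is why item 5 is needed. Counting missing as non-response penalises the arm with more loss: if lost patients respond like the rest, 40% in both arms becomes 0.40 × 0.75 = 30% against 0.40 × 0.90 = 36%. The result should therefore be read beside the table in item 4.

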The aim of this study is to explore the role of the CDED combined with PEN in both inducing and maintaining remission of CD in adults, taking into consideration important objective biomarkers such as faecal calprotectin (FC) (21) along with patient reported outcomes. More precisely, our primary goal is to investigate whether CDED with PEN could lead to a significant decrease in feacal calprotectin concentration. In view of the existing dietary guidelines for adult Crohn's disease patients (7,8) and considering that dairy constitute the main dietary source of calcium, researchers wish to challenge patients in remission with a gradually increasing exposure to dairy products, to assess tolerability, prospecting for the development of a personalized remission maintenance diet based on the CDED principles. Our aim is to examine the proportion of patients with significant feacal inflammation elevation following the dairy introduction.

We intent to investigate the effectiveness and feasibility of this dietary strategy in terms of changes in clinical and biochemical indices, patient's quality of life and nutritional status as well as patients' adherence and acceptance of the diet. Finally, we plan to re-evaluate patients' dietary habits and clinical outcomes, 6 months after the beginning of the study to address the established dietary adaptations, as well as the sustainability and durability of potential benefits of the dietary intervention.

Design and Methods

The proposed project is a randomized controlled clinical trial which is held in Evangelismos General Hospital of Athensin collaboration with the Department of Food Science & Human Nutrition of Agricultural University of Athens. Briefly, eligible patients are adults with established Crohn's disease with ileal and/or colonic involvement who receive their IBD care at the hospital's Gastroenterology Unit (see eligibility criteria below). Patients with active mild-to-moderate disease, defined by aHarvey–Bradshaw Index (HBI) score of 5–14 points, or inactive disease (HBI<5) are eligible for enrolment. Detailed information about the purpose and the study procedures will be given to all patients and consent form will be signed. The study protocol has been approved by the Ethics committee of the hospital.

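### The SAP names no deciding between-arm analysis of faecal calprotectin, the outcome of the primary goal, and never uses baseline calprotectin as a covariate

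*Combined protocol and SAP*

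**What the plan says.** Design and Methods describes the study in these words: "The proposed project is a randomized controlled clinical trial". On allocation it says: "Patients will be randomly assigned 1:1 to either CDED plus PEN plus dairy products or PEN plus usual nutritional care". Both arms therefore receive partial enteral nutrition (PEN). Under Objectives the outcome of main interest is set: "our primary goal is to investigate whether CDED with PEN could lead to a significant decrease in feacal calprotectin concentration". That sentence has no comparator, visit or summary measure.

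The Statistical Analysis Plan section offers four things that could bear on FC:

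- A general list of tests: "Continuous variables will be analyzed by using Mann Whitney U test and t-test for paired-samples or the Wilcoxon signed rank". A normality check comes first, in order "to use parametric or non-parametric tests, as appropriate".
- One sentence that mentions FC by name: "For paired measures (e.g. FC concentration) before and after the intervention, we will calculate the percentage change for each patient relative to baseline". It defines a derived quantity and attaches no test to it.
- Chi-squared or Fisher tests for categorical variables, with no FC category defined.
- Exploratory logistic models with age, sex, disease location and activity, baseline Mediterranean diet score, and then "adherence and intervention grouping would contribute to significant HBI or FC concentration drop".

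Design and Methods lists faecal sampling at baseline, week 4 or 6, and week 8 or 10. Neither follow-up sample is named as primary. The visit description in the same section differs. It calls week 8 or 10 the middle of the study and also has biological samples taken at the end of the study, with the last follow-up at week 24.

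**The concern.** In a randomised trial the primary question should be settled by one designated comparison between the arms. Mann-Whitney is a between-arm test, so the fair reading is that some such comparison is intended. But the SAP does not link it to FC, does not say whether it is applied to percentage change or to the follow-up value, and does not fix the visit. Each of these between-arm readings is valid alone. They can give different verdicts on the same data, and choosing among them afterwards raises the false-positive rate.

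The logistic model cannot fill the gap. The FC drop it models has no cut-off, whereas the HBI response has one (a fall of at least 3). Baseline FC is not among its terms, and activity is defined in the protocol by HBI. It also adjusts for adherence, which arises after randomisation.

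Baseline FC enters only as the denominator of the percentage change. As a covariate it would usually give a more precise comparison at no extra data cost.

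A further risk, though not a stated plan, follows from the goal being worded as a decrease and from paired tests being listed. A before-after fall within the Crohn's Disease Exclusion Diet (CDED) arm could be reported as success. Such a fall would not show a CDED effect, because control patients also receive PEN.

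**Working it through.** **1. The plan's own figure.** The SAP states N = 140, power above 80% and two-sided alpha 0.05. It gives no endpoint, test, effect size, SD or dropout rate, so the figure cannot be reproduced. Solving backwards for 80% power:

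- Two-sample comparison, 70 per arm: d = (1.960 + 0.842) × √(2/70) = 0.474 SD.
- Paired comparison using all 140: n = (2.802/0.237)² ≈ 140, a standardised change of 0.237.
- Two proportions, 70 per arm without continuity correction: for example 30% versus 53%.

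The number 140 fits all three, so it does not reveal which analysis was intended.

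**2. Power of the readings left open.** Assumed, because the documents give none of it: 70 per arm, no dropout, log-normal FC, log SD 1.0-1.3, baseline to follow-up correlation r of 0.3-0.7. The effect is set at 0.477 residual SDs (true ratio of geometric means 0.55-0.71), which gives ANCOVA of log FC about 80% power: Φ(0.477 × √35 − 1.96) = Φ(0.86) ≈ 0.81.

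Percentage change is a monotone function of the log change, so Mann-Whitney on one equals Mann-Whitney on the other. With relative efficiency 0.955 for normal data, power ≈ Φ(δ × √(35 × 0.955) − 1.96), where

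- percentage change: δ = 0.477 × √((1 + r)/2)
- follow-up FC: δ = 0.477 × √(1 − r²)

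| r | % change: formula | % change: simulated | Follow-up: formula | Follow-up: simulated | ANCOVA: simulated |
|---|---|---|---|---|---|
| 0.3 | 0.60 | 0.59 | 0.75 | 0.74 | 0.79 |
| 0.5 | 0.67 | 0.65 | 0.67 | 0.66 | 0.80 |
| 0.7 | 0.72 | 0.71 | 0.50 | 0.49 | 0.80 |

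The simulated columns are for log SD 1.0, with 5,000 trials per setting. At log SD 1.3 they are 0.61/0.67/0.71, 0.75/0.66/0.50 and 0.80/0.80/0.79. Under no effect each method holds its level (Mann-Whitney 0.047-0.055, ANCOVA 0.050-0.053).

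With heavier tails (t, 5 df) Mann-Whitney reaches 66-80% on percentage change and 56-83% on follow-up FC. The loss then vanishes for percentage change at r = 0.7 and for follow-up FC at r = 0.3.

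**3. Cost of leaving the choice open.** 20,000 simulated trials, log SD 1.0, r = 0.3/0.5/0.7:

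- At the effect above, the two Mann-Whitney readings disagree on significance in 30%/31%/40% of trials.
- With no effect, at least one is significant at a single visit in 8.8%/8.9%/9.5%.
- Over two visits (four tests, equal correlations) the figure is 15.8%/16.7%/16.2%.

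One designated test would give 5%.

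**4. Before-after reading.** Assume FC falls by 30% in both arms and CDED adds nothing. The Wilcoxon signed-rank test on raw FC within the CDED arm is then significant in 60%/75%/92% of trials at log SD 1.0 and 40%/52%/71% at 1.3. If only patients with active disease fall by 30% (their baseline assumed 1 log unit higher), it is significant in 8-21%, 16-44% and 25-71% of trials with 30%, 50% and 70% active.

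**The case against.** The strongest reply is that the trial has a valid between-arm test on its list, that omitting baseline FC causes no bias under randomisation, and that percentage change is the only FC summary the SAP names. On that reading Mann-Whitney on percentage change is the intended analysis. The disagreement and 9-10% figures, which need follow-up FC as a second reading, would fall away. The visit might also be inferred: the primary goal concerns CDED with PEN, and the stage before dairy ends at week 4 or 6.

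Much of this is fair. Baseline adjustment is a matter of precision, not validity. Designating Mann-Whitney on percentage change at one visit would also close the main gap. The false-positive figures count both directions: false results favouring CDED run at 4.1-4.5% for either reading at one visit, against 2.5% for one two-sided test. ANCOVA is not always ahead. With heavy tails, or an assumed assay floor at the median with r = 0.3 (Mann-Whitney on follow-up FC 0.61, ANCOVA 0.59), its advantage disappears. The before-after results span 8% to 92% and rest wholly on assumption.

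The gap in designation remains. The percentage-change sentence promises a calculation, not a test. The visit can be argued either way, because the SAP's phrase about before and after the intervention fits week 8 or 10 equally well. A reader who has to infer the primary analysis does not have a pre-specified one.

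**Conclusion.** The concern holds. The textual part is certain: no between-arm FC analysis is designated, and baseline FC is nowhere a covariate. The trial is not invalidated, and no claim is made that 140 is the wrong number. The numerical part is illustrative. Under log-normal FC with r between 0.3 and 0.7, the unadjusted readings give up roughly 5 to 30 percentage points of power against ANCOVA, with the exceptions noted for heavy tails and assay floors. An open choice between two readings roughly doubles the false-positive rate at one visit and about triples it over two. This should be fixed before any outcome data are examined.

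**What to change.** State in the SAP that the primary FC analysis compares the arms by ANCOVA of log FC on arm, log baseline FC and activity group at entry (remission or active), with patients analysed as randomised. Report the ratio of geometric means with its 95% confidence interval. Label percentage change, within-arm paired tests and the logistic model as descriptive or exploratory. Mann-Whitney can stay as a sensitivity analysis.

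Name one primary FC visit, after reconciling the two sampling schedules in Design and Methods, and add a line on missing follow-up FC.

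The cost is low. Baseline FC and activity are already collected, so the model itself needs only wording. The sample size should be restated for the chosen analysis. If 140 was meant for a follow-up difference of 0.474 SD, ANCOVA would need about 70 × (1 − r²) per arm, a total of 128, 106 or 72 at r = 0.3, 0.5 or 0.7 before dropout, so the planned number would suffice on that assumption.

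### As worded, the SAP's percentage-change rule reaches HBI, where it has no value at a baseline of 0 and is unstable at baselines of 1 to 4

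*Combined protocol and SAP*

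**What the plan says.** The only change measure that the Statistical Analysis Plan (SAP) section defines is a percentage: "For paired measures (e.g. FC concentration) before and after the intervention, we will calculate the percentage change for each patient relative to baseline." It makes no exception for HBI and gives no rule for a baseline of zero.

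HBI is a paired measure. Design and Methods, item v, schedules it as "Time Frame: Baseline, week 4/w6, week 8/w10". The same section admits patients with a "score of 5–14 points, or inactive disease (HBI<5) are eligible for enrolment", so there is no lower bound.

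Other provisions treat HBI differently:

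- Item v works in points: "Clinical response is defined as baseline HBI score decrease of ≥ 3".
- For tests, the SAP says "Continuous variables will be analyzed by using Mann Whitney U test and t-test for paired-samples or the Wilcoxon signed rank" and "Chi-squared or Fischer's test will be used to analyze categorical variables".
- A logistic model will explore how baseline factors, adherence and "intervention grouping would contribute to significant HBI or FC concentration drop". It gives no cut-off or scale for that drop.

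The Objectives name a fall in FC as the primary goal, and give both induction and maintenance of remission as the aim.

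**The concern.** A percentage of baseline suits a concentration that is well above zero. HBI is a low-count score, and the design deliberately recruits patients at its lower end. There the divisor is 0 to 4, so the result depends more on the starting score than on what happened to the patient.

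Two things are at stake. First, a patient who starts at 0 has no percentage change at all, whether that patient stays well or relapses. The values lost come from the patients in deepest remission, so the loss is not random. Second, among patients who do have a value, the ordering is wrong: trivial moves at low scores rank above large moves at high scores.

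The 3-point response does not fill the gap for the maintenance aim. It counts falls only, and entrants at 0 to 2 cannot fall by 3. A relapse from 0 is recorded as non-response, the same as staying at 0.

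**Working it through.** **Inputs from the documents.** Total sample 140, allocated 1:1 (70 per arm); two-sided 5% level; baseline HBI below 5 or 5–14; response in points.

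**Assumptions.** The HBI minimum is 0. The share entering in remission and the share of those scoring 0 are not in the documents.

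**The plan's own figure.** The 140 cannot be reproduced, because the SAP gives no effect size, SD, rates, endpoint or dropout. Solving backwards, 70 per arm gives 80% power at a standardised difference of (1.960 + 0.842) × √(2/70) ≈ 0.474. It is used below only as a yardstick.

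**Step 1: the measure.** Percentage change = 100 × (follow-up − baseline) / baseline.

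| HBI move | Points | Percentage change |
|---|---|---|
| 0 to 5 | +5 | undefined (divisor 0) |
| 1 to 5 | +4 | 100 × 4/1 = +400% |
| 4 to 5 | +1 | 100 × 1/4 = +25% |
| 1 to 2 | +1 | 100 × 1/1 = +100% |
| 4 to 6 | +2 | 100 × 2/4 = +50% |
| 1 to 0 | −1 | 100 × (−1)/1 = −100% |
| 14 to 7 | −7 | 100 × (−7)/14 = −50% |

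A score of 5 is the lower limit of active disease. A move from 1 to 2, still in remission, ranks above a move from 4 to 6, which crosses that limit. Opposite moves do not cancel: 1 to 4 (+300%) and 4 to 1 (−75%) average (300 − 75)/2 = +112.5%, although the mean change in points is 0.

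**Step 2: patients without a value.** Number = 140 × remission share × share at 0.

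- Half in remission, 10% at 0: 140 × 0.5 × 0.10 = 7.
- Half in remission, 40% at 0: 140 × 0.5 × 0.40 = 28.
- Wider range, 25–75% in remission and 10–50% at 0: 3.5 to 52.5, or about 4 to 53.

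Power from lost numbers alone, for a comparison using percentage change only at a standardised difference of 0.474, is Φ(0.4736 × √(n/2) − 1.960), with n per arm:

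- 7 lost (n = 66.5): Φ(0.77) ≈ 78%.
- 28 lost (n = 56): Φ(0.55) ≈ 71%.
- Over the wider range: 79% down to 60%.

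**Step 3: relapses without a value.** Assume 35 remission entrants per arm and relapse in 25% and 10%. Expected relapses are 35 × 0.25 + 35 × 0.10 = 12.25. If relapse is unrelated to scoring 0, then 10–40% of them, about 1 to 5, have no percentage value. This restates the assumption; it is not independent evidence.

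**Step 4: power by choice of measure.** Simulated trials had 70 per arm, half in remission with 10, 25 or 40% of those at 0, the relapse rates above, and an extra 2-point fall in active entrants. All of these inputs are assumed.

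| HBI comparison of arms | Power | Power, repeat simulation |
|---|---|---|
| Mann–Whitney on percentage change, zeros dropped | 53–54% | 50–57% |
| Mann–Whitney on change in points | 57–60% | 59–61% |
| Follow-up HBI adjusted for baseline HBI and entry group | 84–87% | 85–87% |

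Moving from percentage to points gains about 3 to 9 points of power. The larger gain comes from the adjustment.

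**The case against.** The strongest reply is that the SAP says only that percentage change will be calculated. It attaches no test to it and does not say that undefined values are excluded. HBI also has its own rule in item v, and a specific rule may be taken to govern over a general sentence whose only example is a concentration. A patient who goes from 0 to 6 keeps a value in a paired test on raw scores, and stays in the denominator of the 3-point response and of a logistic model built on it. This stands. A reader might infer that relapses from HBI 0 drop out of the HBI comparison altogether; the documents do not say so. Nor do they show an outright contradiction with item v, since a response in points and a percentage summary can coexist.

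The reply has limits. The paired tests compare within patients, not between arms. The response counts only falls. The SAP does not say which HBI scale the between-arm test uses.

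A second reply is that Mann–Whitney uses ranks, so the size of a value such as +400% carries no leverage, and the bad ordering matters mainly if remission and active entrants are pooled. The first half is right. On the second, the SAP neither states nor rules out pooling, and the moves 1 to 2 and 4 to 6 are misordered within the remission group alone. The illustration of 1 to 0 outranking 14 to 7 is the extreme case: 2 to 1 only ties with it at −50%, and 3 to 2 (−33%) does not reach it.

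A third reply, that the magnitudes rest on assumed shares and effects, is correct.

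**Conclusion.** The point holds as a fault in the wording of a stated rule. Read literally, the rule reaches HBI, has no value at baseline 0 and is unstable at 1 to 4. The instability remains even if nobody scores 0. The loss of patients at 0 is a risk in any HBI comparison based on percentage change, not a planned exclusion.

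Its size depends on shares that the documents do not give: 7 to 28 patients without a value if half enter in remission and 10–40% of those score 0.

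Two further inferences should be resisted. The rise in power to about 85–87% might be credited to dropping the percentage; nearly all of it comes from adjusting for baseline HBI and entry group. And the point might be extended to IBDQ, albumin, handgrip strength or anthropometry; nothing in the documents shows a zero-baseline problem there.

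HBI is not the primary measure, and the FC goal is unaffected. The change is worth making because it is cheap and HBI bears on the aim of maintaining remission.

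**What to change.** Add one sentence to the SAP: percentage change from baseline is not calculated for HBI; the arms are compared on follow-up HBI in points (week 8 for remission entrants, week 10 for active entrants) by regression adjusted for baseline HBI and entry group (remission or active).

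This keeps every patient with a follow-up score, lets rises count as well as falls, and agrees with the points scale in item v. Change in points without adjustment would also remove the undefined values, but would recover little power.

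The cost is that sentence and one regression model for a non-primary measure. It needs no new data, visits or patients, because baseline HBI and entry group are already recorded.
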